Water Immersion and Polyp Detection: A Randomized Controlled Trial

Edited April 23rd 2019

NCT03231917

Introduction

Although water can be used to facilitate colonoscope insertion¹⁻¹³, the use of two techniques employing water have been evaluated for their effects on adenoma detection as compared to standard insertion methods which employ air or CO₂^{14, 15}. These techniques are called water exchange (WE) and water immersion (WI). In WI, water is used to distend the colon during insertion and is removed largely during withdrawal. WI utilizes enough water during insertion to identify the luminal direction but dirty water is removed primarily during withdrawal. WE is a slower insertion technique in which the air valve is turned off and clean water is infused and dirty water is suctioned during insertion and the instrument is not advanced until the lumen is clean. WE also involves aspiration of retained gas pockets during insertion. Both WE and WI use air or CO₂ rather than water to distend the lumen during withdrawal, and therefore it is not known whether visualization of the mucosa using water as a medium, as opposed to air or CO₂, increases adenoma detection¹⁶. In contrast to the other methods, TUC involves water exchange (WE) during insertion followed by continuous water infusion (rather than gas) on withdrawal in order to distend the lumen for total underwater mucosal visualization.

The use of water during colonoscopy may improve adenoma detection through several possible mechanisms¹⁷. It may help to further clear the bowel of any residual stool. In addition, since water may allow for mucosal inspection without fully distending the lumen like air does, water techniques might increase the yield for flat lesions. Very flat lesions may be less visible with full distention of the lumen. Finally, water has a magnifying effect, which may also increase detection. Thus, TUC, in which the entire procedure including withdrawal is performed underwater, could potentially improve polyp detection compared to gas insufflation.

The goal of our study was to use TUC in tandem with standard CO₂ insufflation to determine if water is a better medium than CO₂ for visualizing and detecting polyps and adenomas. Our goal was to randomize patients to tandem colonoscopy performed first with either TUC or CO₂ followed by the other medium in order to compare miss rates for

polyps and adenomas. Our hypothesis was that TUC was associated with a lower adenoma and polyp miss rate for tandem performance of colonoscopy than CO₂.

Methods

We conducted a randomized trial of tandem colonoscopies comparing TUC to CO₂ insufflation. Our study was approved by the Institutional Review Boards at the White River Junction Veterans Affairs Medical Center and Indiana University. All patients were consented with written consent prior to the colonoscopies. In one group, TUC was employed as the first method for mucosal inspection while in a second group, CO₂ insufflation was used first.

Study Population

Eligible subjects were adults 50-80 years who presented for colonoscopy at White River Junction VAMC, Indianapolis VAMC, and Indiana University. Exclusion criteria included a co-morbid status of American Society of Anesthesiologists physical status classification system ASA of III (severe systemic disease) or higher, Inflammatory Bowel Disease (IBD), surgical resection of the large bowel, as well as the use of non-aspirin anticoagulants. Finally, potential subjects who did not report a clear effluent in the most recent bowel movement at time of colonoscopy were excluded from the study.

Randomization

The participants were randomized using a random number generator, stratified by endoscopist/site. The results of the randomization were opened prior to the initial insertion of the colonoscope, informing the endoscopist which method was first, CO₂ or TUC.

Colonoscopy

Consenting adults were randomized to undergo colonoscopy with either TUC or CO₂ insufflation for the first colonoscopy followed by an examination using the other technique. All examinations were performed by one of three experienced endoscopists ([name], [name], [name]). Participants were sedated using propofol or moderate sedation with midazolam/fentanyl and diphenhydramine. All colonoscopies were performed with high definition colonoscopes. (Olympus CF-HQ190L; Olympus (Tokyo, Japan))

The randomization envelope was opened prior to the initial insertion. An assistant measured the inspection time with a stopwatch from insertion of scope into the rectum until the cecum was reached, stopping the watch during insertion for polyp resection in both techniques or for time spent washing or suctioning (in CO₂ arm only). For the arm where CO₂ insufflation was used first, the lumen was distended with the gas during insertion. When the TUC technique was used first, the air valve was shut off and water was infused and any residual stool or air was suctioned out during insertion. After the cecum was intubated, the endoscopist attempted to intubate the terminal ileum. The mucosal inspection was then initiated during withdrawal when the distention with water or CO₂ was adequate for visualization. Measurement of withdrawal and inspection times was initiated at this point. Inspection time was the withdrawal time minus the time for biopsy or polypectomy or for time spent washing or suctioning (in CO₂ arm only). The assistant with a stopwatch announced the withdrawal time periodically with the goal to equalize inspection times.

When the withdrawal of the colonoscope reached the rectum and after the retroflexion was performed, the endoscopist re-inserted the colonoscope using the other technique. For the exams with TUC as the first method, water was suctioned out of the lumen as CO₂ was introduced into the lumen during the second insertion. Upon withdrawal, the remaining water was aspirated and CO₂ was used to distend the lumen to allow for adequate inspection of the mucosa. In the group in which CO₂ is used first, CO₂ was suctioned out during the second colonoscopy as the scope was inserted with water infusion. As the scope was withdrawn, water was infused with the air valve turned off. Inspection was not started until after cecal intubation and the lumen was filled with water allowing for adequate visualization of the mucosa through the infused water. Inspection time was measured as outlined above.

Outcomes

The primary outcome measure and study endpoint was the miss rate for polyps and adenomas in the two study groups ¹⁸. Miss rates were also calculated for participant level for each technique. Adenoma-level miss rates were calculated as the number of additional adenomas detected during the second examination (for both insertion and withdrawal) divided by the total number of adenomas detected during insertion and

withdrawal for both examinations. These miss rates were reported for the technique used for the first examination. Participant-level miss rates were calculated as the number of participants with one or more adenomas detected during the second examination, divided by the total number of participants with at least one adenoma in either examination. We also examined proximal (cecum, ascending colon, transverse colon and splenic flexure) adenoma miss rates as a secondary outcome, which were calculated as above. Finally, we also calculated serrated polyp (hyperplastic, sessile serrated polyp and traditional serrated adenoma)

For each polyp, we estimated size by open forceps, and noted location, method of removal, whether polyps were detected by insertion or withdrawal and whether CO₂ or TUC was used for mucosal inspection.

We used the Boston Bowel preparation score to assess the quality of the preparation. We also used a scale of good (3), fair (2) and poor (1) to assess the clarity or turbidity of the water during TUC for 3 segments, right, transverse and left colons.

Co-variates

Data collected included participant age and sex, exam indication, personal history of colorectal neoplasia, family history of CRC, time (total procedure, insertion and inspection), volume of water infused during insertion and withdrawal, quality of bowel preparation as measured by the Boston Bowel Preparation Score and medications provided during the procedure.

Statistical considerations

In calculating a sample size required to detect a clinically important difference in miss rates between TUC and CO₂ we used the following assumptions: a 30% adenoma miss rate for regular colonoscopy^{19, 20}; a 10% adenoma miss rate with TUC; 50% of participants would have at least one adenoma, and participants with adenomas would have an average of two adenomas. We based this in part on a tandem study using cap since the cap had similar reported increase in adenoma detection to water exchange¹⁸. For the study to have 80% power to detect a 3-fold reduction in adenoma miss rates, by using a chi-square test with a 5% significance level, the study needed 60 adenomas per group. We assumed that each participant would have on average two polyps and planned to enroll at least 120 participants (60 at each site).

Participants who underwent initial colonoscopy with TUC were compared with participants who underwent colonoscopy with CO₂ first for differences in age and propofol dose by using 2-sample t-tests, for differences in sex and indication by using chi square tests, and for a difference in quality of bowel preparation by using a Mantel-Haenszel test for ordered categories. Logistic regression was used to compare the miss rates between participants who underwent TUC first and participants who underwent CO₂ first. The model was adjusted for participant age, sex, family history of CRC, exam indication, time for inspection, insertion time and volume of water infused/aspirated. A generalized estimating equation was used to control for the effect of the endoscopist.

6. Leung FW. Water exchange may be superior to water immersion for colonoscopy. *Clinical gastroenterology and hepatology : the official clinical practice journal of the American Gastroenterological Association* 2011;9:1012-4.

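### TUC combines water-exchange insertion with water-filled withdrawal, and the miss rate pools both phases, so the trial tests a technique and cannot isolate water as the viewing medium

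*Combined protocol and SAP*

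**What the plan says.** The Introduction notes that earlier water techniques withdrew in gas, so the effect of viewing the mucosa through water is unknown. It then sets the goal: to "determine if water is a better medium than" CO₂. The hypothesis that follows is about the technique: "Our hypothesis was that TUC was associated with a lower adenoma and polyp miss rate".

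The same section defines the intervention as having two parts: "TUC involves water exchange (WE) during insertion followed by continuous water infusion (rather than gas) on withdrawal". Of the first part it says "WE is a slower insertion technique", with the scope held back until the lumen is clean. It lists clearing residual stool as one possible mechanism, beside reduced distension and magnification. Under Colonoscopy, the CO₂-first arm is inserted with gas distension.

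Under Outcomes, the numerator of the adenoma miss rate is the "number of additional adenomas detected during the second examination (for both insertion and withdrawal", and the denominator is all adenomas from both phases of both examinations. The phase in which each polyp was found is recorded, but no listed outcome or analysis uses it. Statistical considerations compares miss rates by logistic regression adjusted for, among other things, inspection time, insertion time and water volume.

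**The concern.** The goal concerns the viewing medium, but the contrast changes three things at once: how the scope is inserted, how well the bowel is cleaned on the way in, and what fills the lumen on the way out. A lower miss rate with TUC could come from any of them. No examination pairs water-exchange insertion with gas withdrawal, so nothing in the design separates them.

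What is at stake is the wording of the conclusion. If a TUC advantage were reported as showing that water is the better medium, the data would not support it, although the advantage itself could be a real difference between techniques.

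**Working it through.** **1. Reproduce the plan's figure.** Inputs from Statistical considerations: miss rates 30% and 10%, chi-square test, 5% level (taken as two-sided), 80% power. With pooled variance and no continuity correction:

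n = [1.96·√(2·0.2·0.8) + 0.842·√(0.21 + 0.09)]² / 0.20² = 61.6, so 62 per group.

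The plan states 60, which gives 78.9% power. With 1:1 allocation assumed, 60 participants × 50% × 2 adenomas = 60 adenomas per arm. The figure reproduces, and this point does not alter it. The planned difference is 20 points.

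**2. What differs between the examinations.**

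| Component | TUC | CO₂ |
|---|---|---|
| Insertion | water exchange, slower | gas |
| Cleansing during insertion | part of the method | not part of the method; washing and suctioning as needed, off the clock |
| Withdrawal medium | water | gas |
| Phases counted | both | both |

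The plan's own effect size points to the insertion component. It is based in part on a cap study, chosen because the cap's reported gain resembled that of water exchange, which by the Introduction withdraws in gas.

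**3. Insertion finds only, media equal.** The documents give no yields, so these are assumptions: CO₂ insertion yield i_C = 5%, TUC insertion yield i_T = 5 to 30%, and the same withdrawal sensitivity w in both media, 60 to 90%. For each technique s = 1 − (1 − i)(1 − w). The miss rates are:

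- CO₂-first = (1 − s_C)·s_T / [1 − (1 − s_T)(1 − s_C)]
- TUC-first = (1 − s_T)·s_C / [1 − (1 − s_T)(1 − s_C)]

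Example, i_T = 30%, w = 60%: s_T = 0.72, s_C = 0.62, denominator 1 − 0.28·0.38 = 0.8936. CO₂-first = 0.2736/0.8936 = 30.6%; TUC-first = 0.1736/0.8936 = 19.4%.

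| i_T | w = 60%: CO₂-first / TUC-first | w = 80% | w = 90% | Gap, points |
|---|---|---|---|---|
| 5% | 27.5 / 27.5 | 16.0 / 16.0 | 8.7 / 8.7 | 0 |
| 10% | 28.2 / 25.9 | 16.1 / 15.1 | 8.7 / 8.2 | 0.5–2.3 |
| 20% | 29.4 / 22.6 | 16.5 / 13.4 | 8.8 / 7.3 | 1.5–6.8 |
| 30% | 30.6 / 19.4 | 16.8 / 11.6 | 8.9 / 6.4 | 2.5–11.2 |

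If w is set so that the CO₂-first rate equals the plan's 30%, TUC-first is 30.0%, 27.4%, 23.0% or 19.1% down the rows. If CO₂ insertion found nothing (i_C = 0), the largest gap would be (0.72 − 0.60)/(1 − 0.28·0.40) = 13.5 points.

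**4. Cleansing only, media equal, no insertion finds.** Assume withdrawal sensitivity of 70% before water exchange and c after it, in either medium. CO₂-first = 0.3c/(0.7 + 0.3c); TUC-first = (1 − c)c/[c + (1 − c)c].

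| c | CO₂-first | TUC-first | Gap, points |
|---|---|---|---|
| 75% | 24.3% | 20.0% | 4.3 |
| 80% | 25.5% | 16.7% | 8.9 |
| 85% | 26.7% | 13.0% | 13.7 |
| 90% | 27.8% | 9.1% | 18.7 |

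**5. Both at the top of their ranges.** Take i_C = 5%, i_T = 30%, w = 70% before cleansing and 90% after.

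- CO₂-first: the first examination finds 1 − 0.95·0.30 = 0.715 and the second 1 − 0.70·0.10 = 0.93 of the rest. Miss rate 0.285·0.93/(0.715 + 0.285·0.93) = 27.0%.
- TUC-first: the first finds 0.93 and the second 1 − 0.95·0.10 = 0.905 of the rest. Miss rate 0.07·0.905/(0.93 + 0.07·0.905) = 6.4%.

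The gap is 20.7 points, so these inputs give no bound below 20 for the whole bundle.

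**6. Would a phase-specific rate isolate the medium?** Take second-examination adenomas divided by first-withdrawal plus second-examination adenomas, again with equal media.

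- If cleansing raises only TUC's own withdrawal sensitivity from 80% to 85% (i_T = 10%, i_C = 5%): TUC-first = 0.15·0.81/(0.85 + 0.15·0.81) = 12.5%; CO₂-first = 0.20·0.865/(0.80 + 0.20·0.865) = 17.8%. This favours TUC.
- If half the lesions are easy and half hard (withdrawal 95% and 50% in both media; insertion 50% and 10% with TUC, 10% and 0% with CO₂): TUC-first is 21.2% and CO₂-first 19.1%. This favours CO₂.

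The bias can go either way, so such a rate can only be descriptive.

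**The case against.** The strongest reply is that the plan is coherent at the level of the technique. Hypothesis, endpoint and sample size all concern TUC against CO₂. The Introduction also uses the word medium loosely, as a label for whichever technique comes second, and it lists stool clearance among the ways water may help, so cleansing might be seen as part of the question. Several provisions narrow the rival explanations: washing and suctioning in the CO₂ arm, the clear-effluent entry rule, the aim of equal inspection times, and recorded and compared preparation quality. Insertion finds may also be few: "The mucosal inspection was then initiated during withdrawal", and for the second, underwater examination "Inspection was not started until after cecal intubation".

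Much of this stands. The technique-level inference is sound, and low insertion yields are plausible, which is why the first table starts at zero. It does not remove the point. The stated gap in knowledge is that earlier water techniques withdrew in gas, and that gap can only concern the viewing medium. Insertion finds still count in the endpoint, and cleansing can act on withdrawal even if insertion finds nothing.

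A reader might go further and infer that the primary comparison is invalid, that insertion finds say nothing about the medium, or that the authors have already overclaimed. The documents support none of these. Randomisation supports the technique contrast. Lesions seen during TUC insertion are also seen through water ("TUC, in which the entire procedure including withdrawal is performed underwater"). No conclusion from results is stated.

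**Conclusion.** The point holds as a limit on interpretation, and it is minor. The randomised comparison, without adjustment for insertion time, inspection time and water volume, answers the hypothesis about TUC as a technique. It cannot attribute a difference to the viewing medium. Adjusting for those three variables does not isolate the medium either: they arise after randomisation and partly result from the technique, so adjustment may remove part of the technique effect.

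The size is unknown. With equal media and assumed inputs, insertion finds alone give TUC an advantage of 0 to about 11 points (5% CO₂ insertion yield), and cleansing alone gives 4 to about 19. These would be real differences between techniques, not false positives of the planned test. A reader might infer either that the bundle must fall short of the planned 20 points or that it explains all of any effect; the documents support neither.

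**What to change.** Keep the primary endpoint. State the goal and the conclusion as the effect of the whole TUC technique (water-exchange insertion plus water-filled withdrawal) against CO₂, and say that the design does not separate insertion cleansing from the withdrawal medium. Do not present the adjusted model as isolating the medium.

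From the phase already recorded for each polyp, add a descriptive table of adenoma counts by phase, arm and examination. A first-withdrawal miss rate is optional. If given, it should be labelled descriptive, and post hoc if data have been seen, and no claim about the medium should rest on it. Full separation would need the same insertion method in both arms, which is a different trial.

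The cost is one extra table and a narrower claim; enrolment, endpoint and data collection do not change. The question about the medium may stay open.

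### Does leaving the hepatic flexure out of the list that defines proximal colon undermine the secondary proximal adenoma miss rate?

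*Combined protocol and SAP*

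**What the plan says.** The Outcomes section lists "proximal (cecum, ascending colon, transverse colon and splenic flexure) adenoma miss rates as a secondary outcome". The wording has no term such as including or for example, so the four sites read as a complete list. One flexure is named and the other is not.

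The proximal rates follow the rules given just before for the whole colon: "adenoma miss rates as a secondary outcome, which were calculated as above". The adenoma-level rule begins "Adenoma-level miss rates were calculated as the number of additional adenomas detected during the second examination" and divides by all adenomas found in both examinations. A participant-level rule follows it.

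On recording, the same section says only "For each polyp, we estimated size by open forceps, and noted location, method of removal". It gives no code list and no segment boundaries. The one other division of the colon in the document is "for 3 segments, right, transverse and left colons". It grades water clarity during total underwater colonoscopy (TUC), not lesion location, and it places neither flexure.

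**The concern.** A definition written as a closed list invites literal programming. If the polyp form had its own entry for the hepatic flexure, one analyst would apply the four sites as written and drop those lesions. Another would follow the anatomy and keep them. The same data would then give two proximal miss rates. Naming the splenic flexure separately from the transverse colon makes it conceivable that flexures had codes of their own.

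Under that reading the lesions leave the numerator and the denominator together. A participant whose only proximal adenoma lay at the hepatic flexure would also leave the denominator of any participant-level proximal rate. At stake is the precision of one secondary outcome and, if the flexure behaves differently from its neighbours, some shift in its value.

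**Working it through.** **The plan's own figure.** Statistical considerations assumes miss rates of 30% (CO₂) and 10% (TUC), a chi-square test at 5% and 80% power, and concludes that "the study needed 60 adenomas per group". The usual two-sided formula without continuity correction, with mean rate 0.20, gives

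n = [1.96 × √(2 × 0.20 × 0.80) + 0.842 × √(0.30 × 0.70 + 0.10 × 0.90)]² / 0.20² ≈ 62 per group.

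Power at 60 is 78.9%, so the stated figure reproduces closely. It concerns adenomas in the whole colon. No power is stated for the proximal outcome, so the definition of proximal does not enter it.

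**Is the hepatic flexure excluded?** In anatomical order the list starts at the cecum, passes through the ascending and transverse colon, and ends at the splenic flexure. The hepatic flexure joins the second and third of these. To exclude it, an analyst would have to call a lesion non-proximal although the bowel on both sides of it is proximal. The splenic flexure is the far end of the stretch, where inclusion is a real question and has to be stated. An interior bend raises no such question.

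**Size under the literal reading.** The document gives no counts by segment, so three inputs are assumptions: the proximal share (half), the share of proximal adenomas coded separately as hepatic flexure (5-15%), and the miss rate there.

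- Proximal adenomas per group: 60 × 0.5 = 30.
- Dropped: 30 × 0.05 = 1.5 to 30 × 0.15 = 4.5. Remaining: 28.5 to 25.5.
- Expected misses dropped: 0.15-0.45 at a 10% miss rate, 0.45-1.35 at 30%.
- Standard error ratio: √(30/28.5) = 1.026 to √(30/25.5) = 1.085.
- 95% half-width of the difference, treating adenomas as independent: 1.96 × √[(0.10 × 0.90 + 0.30 × 0.70)/n].

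| Adenomas per group | Half-width (percentage points) |
|---|---|
| 30 | 19.6 |
| 28.5 | 20.1 |
| 25.5 | 21.3 |

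With a proximal share of 50-70%, 1.5-6.3 adenomas per group are dropped, and power for 30% versus 10% in the subset falls by about 2 to 7 points. It is low to begin with, at 49% to 63%.

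**Shift in the rate.** With the flexure included, the rate is (1 − s) × 0.30 + s × f, where s is the flexure share and f its miss rate.

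- f = 0.30: the rate stays at 30% for any s.
- f = 0.10 to 0.50: 29-31% at s = 0.05, and 27-33% at s = 0.15.

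**Shift in the comparison.** Suppose lesions at the flexure are missed twice as often in both groups and s = 0.15. The rates with the flexure included are 0.85 × 30% + 0.15 × 60% = 34.5% and 0.85 × 10% + 0.15 × 20% = 11.5%. Their ratio is still 3. Their difference is 23 points instead of 20, a gap of 3 points against a half-width of about 20.

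**The case for a change.** The best argument for a change is that a written definition should not depend on the reader's anatomy. The list is closed, it names one flexure, and no code list or mapping rule fills the gap. With three endoscopists at several sites, uniform coding cannot be taken from the text. Two added words would settle the matter, and no new data are needed because location is already recorded for every polyp.

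The textual part of this stands: the hepatic flexure is absent, and the document does not say how such lesions were coded. The step to a harm does not. Uneven coding among endoscopists matters only if the analyst then leaves a hepatic-flexure code out of the proximal group, and the sense of the list points the other way. If the lesions were entered as ascending or transverse colon, the effect is zero. A code list would commonly sit on the data form, which is not part of this document, so its absence here says little. That a correction is cheap does not show that the outcome is at risk.

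The participant-level argument adds little. The sentence speaks of proximal adenoma miss rates and does not clearly commit to a participant-level version.

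**Conclusion.** The omission is real and is most likely a drafting slip. It needs no change to the plan, because the natural reading of a continuous stretch from cecum to splenic flexure already takes in the hepatic flexure, and analysts would fill the gap that way.

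If the list were applied literally to separately coded lesions, the standard error of each proximal rate would rise by 2.6-8.5%, given a half-proximal share and a 5-15% flexure share. The same rule would apply to both groups, with no expected shift unless miss rates at the flexure differ from those elsewhere in the proximal colon. Those shares are assumptions, and nothing in the document shows that any lesion was lost. The primary miss rate and the 60 adenomas per group do not depend on the point.

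### The 80% power assumes independent adenomas, but the planned 60 per group come from about 30 participants, and the participant is a cluster in neither the sample size nor the model

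*Combined protocol and SAP*

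**What the plan says.** The sample-size paragraph under Statistical considerations compares a 30% adenoma miss rate for standard colonoscopy with 10% for TUC. The target is set in these words: "For the study to have 80% power to detect a 3-fold reduction in adenoma miss rates", and the result follows: "by using a chi-square test with a 5% significance level, the study needed 60 adenomas per group". To turn adenomas into people it assumes "50% of participants would have at least one adenoma, and participants with adenomas would have an average of two adenomas", and it "planned to enroll at least 120 participants".

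The Outcomes section defines the powered quantity per lesion: "Adenoma-level miss rates were calculated as the number of additional adenomas detected during the second examination", divided by all adenomas found at both examinations. A participant-level rate is also defined, but no power is given for it. Randomization is by participant.

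For the analysis, the same Statistical considerations section names an adjusted logistic regression and adds: "A generalized estimating equation was used to control for the effect of the endoscopist". The Colonoscopy section says "All examinations were performed by one of three experienced endoscopists". An ICC, a design effect or an independence assumption appears nowhere, and the participant is not named as a cluster.

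**The concern.** The trial randomizes participants and counts adenomas. Two adenomas in the same colon are seen through the same preparation, by the same endoscopist, with the same first technique and in the same inspection period, so missing one is likely to go with missing the other. If so, 60 adenomas from 30 people carry less information than 60 from 60 people.

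Two things are at stake. The 80% is the only figure that justifies the trial's size, and it would be overstated. And if the primary comparison treats adenomas as independent, its p-value is too small and its confidence interval too narrow.

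**Working it through.** **Inputs from the documents.** Miss rates 0.30 and 0.10; 5% level (taken as two-sided, since sidedness is not stated); 80% power; 50% of participants affected; mean of two adenomas in those affected; 120 participants in two groups (taken as equal); three endoscopists.

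**Assumed.** The within-participant ICC is not given. A range of 0.05 to 0.3 is shown.

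**1. The plan's own figure.** With independent adenomas, difference 0.20, mean rate 0.20, and z-values 1.960 and 0.842:
- Pooled: n = [1.960·√(2·0.2·0.8) + 0.842·√(0.3·0.7 + 0.1·0.9)]² / 0.2² = 61.6 per group.
- Unpooled: n = (1.960 + 0.842)²·(0.21 + 0.09) / 0.2² = 58.9 per group.
- Arcsine: 59.0 per group.

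Power at 60 per group is 78.9% (pooled), 80.7% (unpooled) and 80.2% (exact enumeration of the chi-square test). The stated 60 therefore reproduces under independence, with almost nothing to spare.

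**2. How many people carry these adenomas.** 120/2 = 60 participants per group; 60 × 0.5 = 30 affected; 30 × 2 = 60 adenomas.

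**3. Power with correlation.** The design effect is 1 + (m − 1)·ICC, where m is E[size²]/E[size].
- Exactly two adenomas each: m = 2, design effect 1 + ICC.
- Sizes varying around a mean of two (zero-truncated Poisson, an assumption): m = 2.594, design effect 1 + 1.594·ICC.

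The effective number per group is 60 divided by the design effect. Power is given as pooled to unpooled.

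| ICC | Two each: effective n | Power | Varying: effective n | Power |
|---|---|---|---|---|
| 0 | 60.0 | 79–81% | 60.0 | 79–81% |
| 0.05 | 57.1 | 77–79% | 55.6 | 76–78% |
| 0.1 | 54.5 | 75–77% | 51.8 | 73–75% |
| 0.2 | 50.0 | 71–73% | 45.5 | 67–69% |
| 0.3 | 46.2 | 68–70% | 40.6 | 62–64% |

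To offset an ICC of 0.2, the plan's 60 would become 60 × 1.2 = 72 (two each) or 60 × 1.319 = 79 (varying) adenomas per group.

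**4. Simulation.** With beta-binomial misses and 30 affected participants per group, a test clustered on participant had power of about 73–76%, 68–74% and 63–70% at ICC 0.1, 0.2 and 0.3, which agrees reasonably with the table.

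**5. Type I error if the participant is ignored.** For the plain chi-square test it is about 6–8%, 7–9% and 9–11% at ICC 0.1, 0.2 and 0.3. The lower ends are for exactly two adenomas each; exact calculation for 30 such pairs per group gives 6.2–6.4%, 7.4–7.7% and 8.6–8.9% over common miss rates of 10% to 30%.

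**6. Whether the endoscopist GEE covers it.** Participants are nested within endoscopist, so a robust variance clustered on endoscopist would in principle absorb correlation within participants. With three clusters it is unreliable: simulated type I error with an uncorrected robust variance was about 25%, even at ICC 0. Clustering on participant with endoscopist as a fixed factor, and no other covariates, gave 4–5%.

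**The case against.** **The row unit of the model is never stated.** The covariates are all at participant or procedure level, and the text speaks of comparing participants. With one row per participant, correlation between adenomas would not arise in the model. The plan should indeed say which it is. But Outcomes presents the participant-level rate as an addition, and the sample size counts adenomas, so the powered comparison is per lesion. The sample-size point stands under either reading.

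**The type I error figures are for a chi-square test, which the plan uses only for sizing.** This is fair. They show what ignoring the participant costs and are not a forecast for the adjusted model. The 25% for three endoscopist clusters is a separate, few-clusters problem, and it assumes an uncorrected robust variance that the plan does not specify. It shows only that the stated GEE cannot be relied on to cover the gap.

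**The ICC is unknown and may be small.** This also stands. Requiring clear effluent at entry and adjusting for covariates may lower it. At 0.05 with two adenomas each the loss is about 2 points. Power drops below 80% at an ICC of about 0.01 to 0.02 on the unpooled or arcsine formula, but that crossing has little practical meaning; on the pooled formula power is below 80% from the start.

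**There may be more lesions than 60 per group.** The enrolment figure is a minimum, and the same paragraph assumes two polyps per participant, or 120 polyps per group. That could give slack for the polyp miss rate if similar rates apply. It does not help adenomas: the stated assumptions give 0.5 × 2 = 1 adenoma per enrolled participant. No higher target is set.

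**The simulated error rates used no further covariates.** The planned rates imply about 18 + 6 = 24 missed adenomas, against treatment, seven listed covariates and two endoscopist terms, on about 60 participants. The 4–5% is therefore not shown to carry over to the fully adjusted model.

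**Conclusion.** The concern holds. The arithmetic behind 60 adenomas per group is sound, but it rests on an independence assumption that the plan does not state and that its own figures make doubtful: about 30 participants supply the 60 adenomas in each group. At the minimum of 120 participants, power is about 80% at ICC 0 and about 62% to 77% for an assumed ICC of 0.1 to 0.3, the lower values applying when the number of adenomas varies between participants. These figures rest on that assumed range, equal groups, a two-sided test and the plan's own miss rates and prevalence. The GEE as described, on three endoscopists, does not reliably supply the missing protection. The loss is small if the ICC is near 0.05 and material from about 0.1 upward.

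**What to change.** Keep the planned enrolment and change two places in Statistical considerations.

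1. **Sample-size paragraph.** State that power is about 80% if adenomas within a participant are independent, and about 62% to 77% for an assumed within-participant ICC of 0.1 to 0.3 at the minimum of 120 participants.
2. **Analysis paragraph.** State that the primary miss-rate model has one row per adenoma, fitted as a logistic model by GEE clustered on participant, with endoscopist as a fixed factor (three levels, matching the randomization stratum). Because the affected participants are few relative to the covariates listed, it is sensible to say also whether a small-sample variance correction is used.

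The cost is one or two sentences in each place. No added participants or data are needed. The downside is a less favourable stated power and possibly slightly wider confidence intervals.
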